#### 10.1.3 Expectedness

Adverse events can be 'Expected' or 'Unexpected.'

##### 10.1.3.1 Expected adverse event

Expected adverse events are those that have been previously identified as resulting from administration of the agent. For the purposes of this study, an adverse event is considered expected when it appears in the current adverse event list, the Investigator's Brochure, the package insert or is included in the informed consent document as a potential risk.

Refer to Section 6.1 for a listing of expected adverse events associated with the study agent(s).

##### 10.1.3.2 Unexpected adverse event

For the purposes of this study, an adverse event is considered unexpected when it varies in nature, intensity or frequency from information provided in the current adverse event list, the Investigator's Brochure, the package insert or when it is not included in the informed consent document as a potential risk.

#### 10.1.4 Attribution

Attribution is the relationship between an adverse event or serious adverse event and the study treatment. Attribution will be assigned as follows:

- Definite – The AE is clearly related to the study treatment.
- Probable – The AE is likely related to the study treatment.
- Possible – The AE may be related to the study treatment.
- Unlikely - The AE is doubtfully related to the study treatment.

- Unrelated - The AE is clearly NOT related to the study treatment.

## 10.2 Procedures for AE and SAE Recording and Reporting

Participating investigators will assess the occurrence of AEs and SAEs at all participant evaluation time points during the study. AEs related to study treatment will be followed at Long Term Follow-up visits.

All AEs and SAEs whether reported by the participant, discovered during questioning, directly observed, or detected by physical examination, laboratory test or other means, will be recorded in the participant's medical record and on the appropriate study-specific case report forms.

The descriptions and grading scales found in the revised NCI Common Terminology Criteria for Adverse Events (CTCAE) version 4.0 will be utilized for AE reporting. All appropriate treatment areas should have access to a copy of the CTCAE version 4.0. A copy of the CTCAE version 4.0 can be downloaded from the CTEP website at:

[http://ctep.cancer.gov/protocolDevelopment/electronic\\_applications/ctc.htm](http://ctep.cancer.gov/protocolDevelopment/electronic_applications/ctc.htm)

## 10.3 Reporting Requirements

For multi-site trials where a DF/HCC investigator is serving as the principal investigator, each participating investigator is required to abide by the reporting requirements set by the DF/HCC. The study must be conducted in compliance with FDA regulations, local safety reporting requirements, and reporting requirements of the principal investigator.

Each investigative site will be responsible to report SAEs that occur at that institution to their respective IRB. It is the responsibility of each participating investigator to report serious adverse events to the study sponsor and/or others as described below.

## 10.4 Reporting to the Study Sponsor

### 10.4.1 DF/HCC Reportable Adverse Event Reporting

In addition to SAEs that meet criteria from section 10.1.2, the Sponsor requires additional events to be reported to the Coordinating Center. All DF/HCC reportable adverse events that occur after the initial dose of study treatment, during treatment, or within 30 days of the last dose of treatment must be reported to the Coordinating Center on the local institutional SAE form. This includes the following:

- Grade 2 (moderate) and Grade 3 (severe) Events events that are unexpected and considered possibly, probably or definitely related/associated with the intervention.

**Note:** Grade 2 or 3 neutropenia, leukopenia, and lymphopenia are expected with chemotherapy in this patient population and are not required to be reported.

- All Grade 4 (life-threatening or disabling) Events – Unless specifically listed in the protocol as not requiring reporting.

**Note:** Grade 4 neutropenia, leukopenia, and lymphopenia are expected with chemotherapy in this patient population and are not required to be reported.

- All Grade 5 (fatal) Events – When the participant is enrolled and actively participating in the trial OR when the event occurs within 30 days of the last study intervention.

**Note:** If the participant is in long term follow up, report the death at the time of continuing review.

Due to the additional expedited reporting criteria, the table below is a tool to summarize the reporting requirements and timelines for SAEs and DF/HCC reportable adverse events to the Coordinating Center.

[figure not shown]
Attribution	SAEs	DF/HCC Reportable AEs				
	All SAEs (section 11.1.2)	Gr. 2 & 3 AE Expected #	Gr. 2 & 3 AE Unexpected #	Gr. 4 AE Expected #	Gr. 4 AE Unexpected #	Gr. 5 AE Expected or Unexpected
Unrelated Unlikely	1 business day	Not required	Not required	5 calendar days*	5 calendar days*	1 business day
Possible Probable Definite	1 business day	Not required	5 calendar days	5 calendar days*	5 calendar days*	1 business day

# If event meets SAE criteria listed in section 10.1.2 in addition to grade, attribution and expectedness, event must be reported within 24 hours.

\* If listed in protocol as expected and not requiring reporting, event does not need to be reported.

Participating investigators must report each serious adverse event to the Coordinating Center in accordance with the table above. In the event that the participating investigator does not become aware of the serious adverse event immediately (e.g., participant sought treatment elsewhere) or within the reporting timeframes listed in the table above, the participating investigator is to report the event within 1 business day after learning of it and document the time of his or her first awareness of the adverse event. Report serious adverse events by telephone, email or facsimile to:

Coordinating Center

Within the following 1-2 business days, the participating investigator must provide follow-up information on the serious adverse event. Follow-up information should describe whether the event has resolved or continues, if and how the event was treated, and whether the participant will continue or discontinue study participation.

#### 10.4.2 Non-Serious Adverse Event Reporting

Non-serious adverse events will be reported to the Coordinating Center on the toxicity Case Report Forms.

#### 10.5 Reporting to the Institutional Review Board (IRB)

Investigative sites within DF/HCC will report all serious adverse events directly to the DFCI Office for Human Research Studies (OHRS).

External Participating Sites should report serious adverse events to their respective IRB according to the local IRB's policies and procedures in reporting adverse events. A copy of the submitted institutional SAE form should be forwarded to:

Coordinating Center  

The Coordinating Center will submit SAE reports from outside institutions to the DFCI Office for Human Research Studies (OHRS) according to DFCI IRB policies and procedures in reporting adverse events.

#### 10.6 Reporting to the Food and Drug Administration (FDA)

The DF/HCC Overall Principal Investigator, as holder of the IND, will be responsible for all communication with the FDA. The Coordinating Center will report to the FDA, regardless of the site of occurrence, any adverse event that is serious, unexpected and reasonably related (i.e., possible, probable, definite) to the study treatment.

Unexpected fatal or life-threatening experiences associated with the use of the study treatment will be reported to FDA as soon as possible but in no event later than 7 calendar days after initial receipt of the information.

All other serious unexpected experiences associated with the use of the study treatment will be reported to FDA as soon as possible but in no event later than 15 calendar days after initial receipt of the information.

#### 10.7 Reporting to Seattle Genetics

The participating investigator must report each serious adverse event, regardless of attribution, to the Coordinating Center within 1 business day of learning of the occurrence. In the event that the participating investigator does not become aware of

the serious adverse event immediately (e.g., participant sought treatment elsewhere), the participating investigator is to report the event within 1 business day after learning of it and document the time of his or her first awareness of the adverse event. Report serious adverse events by facsimile to:

Coordinating Center Fax: [REDACTED]

The Coordinating Center will be responsible for forwarding all serious adverse events to Seattle Genetics Drug Safety Department [REDACTED] within 30 days of receiving the initial fax notification from participating investigators. Events meeting FDA reporting criteria (see 11.6) will be reported to Seattle Genetics Drug Safety at the same time the FDA is notified by the Coordinating Center.

#### **10.8 Reporting to Hospital Risk Management**

Participating investigators will report to their local Risk Management office any subject safety reports or sentinel events that require reporting according to institutional policy.

#### **10.9 Monitoring of Adverse Events and Period of Observation**

All adverse events, both serious and non-serious, and deaths that are encountered from initiation of study intervention, throughout the study, and within 30 days of the last study intervention should be followed to their resolution, or until the participating investigator assesses them as stable, or the participating investigator determines the event to be irreversible, or the participant is lost to follow-up. The presence and resolution of AEs and SAEs (with dates) should be documented on the appropriate case report form and recorded in the participant's medical record to facilitate source data verification.

For some SAEs, the Principal Investigator/Sponsor or designee may follow-up by telephone, fax, and/or monitoring visit to obtain additional case details deemed necessary to appropriately evaluate the SAE report (e.g., hospital discharge summary, consultant report, or autopsy report).

Participants should be instructed to report any serious post-study event(s) that might reasonably be related to participation in this study. Participating investigators should notify the Coordinating Center and their respective IRB of any unanticipated death or adverse event occurring after a participant has discontinued or terminated study participation that may reasonably be related to the study.

### **11. DATA AND SAFETY MONITORING**

#### **11.1 Data Reporting**

##### **11.1.1 Method**

The QACT and the Coordinating Center will collect, manage, and perform quality checks on the data for this study.

##### **11.1.2 Data Submission**

---

CONFIDENTIAL

This document is confidential. Do not disclose or use except as authorized.

The schedule for completion and submission of case report forms (paper or electronic) to the QACT is as follows:

Form	Submission Timeline
Eligibility Checklist	Complete prior to registration with QACT
On Study Form	Within 14 days of registration
Baseline Assessment Form	Within 14 days of registration
Treatment Form	Within 10 days of the last day of the cycle
Adverse Event Report Form	Within 10 days of the last day of the cycle
Response Assessment Form	Within 10 days of the completion of the cycle required for response evaluation
Off Treatment/Off Study Form	Within 14 days of completing treatment or being taken off study for any reason
Follow up/Survival Form	Within 14 days of the protocol defined follow up visit date or call

## 11.2 Safety Meetings

The DF/HCC Data and Safety Monitoring Committee (DSMC) will review and monitor toxicity and accrual data from this trial. The committee is composed of clinical specialists with experience in oncology and who have no direct relationship with the study. Information that raises any questions about participant safety will be addressed with the Principal Investigator/Sponsor and study team.

The DSMC will meet quarterly and/or more often if required to review toxicity and accrual data. Information to be provided to the committee may include: up-to-date participant accrual; current dose level information; DLT information; all grade 2 or higher unexpected adverse events that have been reported; summary of all deaths occurring within 30 days for Phase I or II protocols; for gene transfer protocols, summary of all deaths while being treated and during active follow-up; any response information; audit results, and a summary provided by the study team. Other information (e.g. scans, laboratory values) will be provided upon request.

## 11.3 Monitoring

Involvement in this study as a participating investigator implies acceptance of potential audits or inspections, including source data verification, by representatives designated by the Principal Investigator/Sponsor or Coordinating Center. The purpose of these audits or inspections is to examine study-related activities and documents to determine whether these activities were conducted and data were recorded, analyzed, and accurately reported in accordance with the protocol, institutional policy, and any applicable regulatory requirements.

All data will be monitored for timeliness of submission, completeness, and adherence to protocol requirements. Monitoring will begin at the time of participant registration and will continue during protocol performance and completion.

## 12. REGULATORY CONSIDERATIONS

### 12.1 Protocol Review and Amendments

This protocol, the proposed informed consent and all forms of participant information related to the study (e.g., advertisements used to recruit participants) and any other necessary documents must be submitted, reviewed and approved by a properly constituted IRB governing each study location.

Any changes made to the protocol must be submitted as amendments and must be approved by the IRB prior to implementation. Any changes in study conduct must be reported to the IRB. The Principal Investigator/Sponsor or Coordinating Center will disseminate protocol amendment information to all participating investigators.

All decisions of the IRB concerning the conduct of the study must be made in writing.

### 12.2 Informed Consent

All participants must be provided a consent form describing this study and providing sufficient information for participants to make an informed decision about their participation in this study. The formal consent of a participant, using the IRB approved consent form, must be obtained before the participant is involved in any study-related procedure. The consent form must be signed and dated by the participant or the participant's legally authorized representative, and by the person obtaining the consent. The participant must be given a copy of the signed and dated consent document. The original signed copy of the consent document must be retained in the medical record or research file.

### 12.3 Ethics

This study is to be conducted according to the following considerations, which represent good and sound research practice:

- US Code of Federal Regulations (CFR) governing clinical study conduct and ethical principles that have their origin in the Declaration of Helsinki
  - Title 21 Part 50 – Protection of Human Subjects  
[www.access.gpo.gov/nara/cfr/waisidx\\_02/21cfr50\\_02.html](http://www.access.gpo.gov/nara/cfr/waisidx_02/21cfr50_02.html)
  - Title 21 Part 54 – Financial Disclosure by Clinical Investigators  
[www.access.gpo.gov/nara/cfr/waisidx\\_02/21cfr54\\_02.html](http://www.access.gpo.gov/nara/cfr/waisidx_02/21cfr54_02.html)
  - Title 21 Part 56 – Institutional Review Boards  
[www.access.gpo.gov/nara/cfr/waisidx\\_02/21cfr56\\_02.html](http://www.access.gpo.gov/nara/cfr/waisidx_02/21cfr56_02.html)

---

CONFIDENTIAL

This document is confidential. Do not disclose or use except as authorized.

- Title 21 Part 312 – Investigational New Drug Application  
[www.access.gpo.gov/nara/cfr/waisidx\\_02/21cfr312\\_02.html](http://www.access.gpo.gov/nara/cfr/waisidx_02/21cfr312_02.html)

- State laws
- DF/HCC research policies and procedures  
<http://www.dfhcc.harvard.edu/clinical-research-support/clinical-research-unit-cru/policies-and-procedures/>

It is understood that deviations from the protocol should be avoided, except when necessary to eliminate an immediate hazard to a research participant. In such case, the deviation must be reported to the IRB according to the local reporting policy.

#### 12.4 Multicenter Guidelines

This protocol will adhere to the policies and requirements of the DF/HCC Multi-Center Data and Safety Monitoring Plan. The specific responsibilities of the Overall PI, Coordinating Center, and Participating Institutions and the procedures for auditing are presented in Appendix E.

- *The Overall PI/Coordinating Center is responsible for distributing all IND Action Letters or Safety Reports to all participating institutions for submission to their individual IRBs for action as required.*
- *Mechanisms will be in place to ensure quality assurance, protocol compliance, and adverse event reporting at each site.*
- *Except in very unusual circumstances, each participating institution will order the study agent(s) directly from supplier. A participating site may order the agent(s) only after the initial IRB approval for the site has been forwarded to the Coordinating Center.*

#### 12.5 Study Documentation

The investigator must prepare and maintain adequate and accurate case histories designed to record all observations and other data pertinent to the study for each research participant. This information enables the study to be fully documented and the study data to be subsequently verified.

Original source documents supporting entries in the case report forms include but are not limited to hospital records, clinical charts, laboratory and pharmacy records, recorded data from automated instruments, microfiches, photographic negatives, microfilm or magnetic media, and/or x-rays.

#### 12.6 Records Retention

---

CONFIDENTIAL

This document is confidential. Do not disclose or use except as authorized.

All study-related documents must be retained for the maximum period required by applicable federal regulations and guidelines or institutional policies.

### 13. STATISTICAL CONSIDERATIONS

#### 13.1 Study Design/Endpoints

This is an open label single arm phase II study to assess the efficacy and safety of brentuximab in combination with Adriamycin and Dacarbazine (AD) in previously untreated stage I and II non-bulky cHL. Brentuximab and AD are administered administered on days 1 and 15 of each 28 day cycle. Interim restaging PET-CT will be performed following cycle 2. Patients with progressive disease will be taken off study. Patients in CR will receive a total of 4 cycles of therapy; patients with stable disease or partial response will receive a total of 6 cycles.

##### 13.1.1 Primary Endpoint and Sample Size

The primary endpoint of this study is complete response rate at EOT restaging. A one-stage design is used. A total of 34 participants will be entered on this study. The expected accrual is 1-2 participants per month. If at least 91% (31) of evaluable participants achieve complete responses, the treatment will be considered promising and worthy of further study. Patients removed from study prior to initial restaging for reasons other than disease progression are not considered evaluable for response. The study has 91% power and 0.09 one-sided type I error to test a CR rate of 95% vs. a CR rate of 81%. With 34 eligible patients the 90% confidence interval for the true response rate will be no wider than 30%. If greater than 2 evaluable participants are seen not to have disease response (CR or PR) following brentuximab-AD therapy, the study will stop. Assuming the null response rate of 81%, the study will stop early with a maximum probability of 0.97. Under the promising rate, the study will stop early with a maximum probability of 0.24.

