## 5.3 Criteria for Removal from Study Treatment

Participants will be removed from study treatment when intercurrent illness, toxicity, inability to participate or a change in condition occurs. The reason for treatment removal and the date the participant was removed must be documented in the study-specific case report form (CRF). Alternative care options will be discussed with the participant.

In the event of unusual or life-threatening complications, participating investigators must immediately notify the Principal Investigator/Sponsor, [name] at [contact].

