## 5.5 Criteria for Removal from Study

Participants will be removed from the study upon death or withdrawal of consent. The reason for study removal and the date the participant was removed must be documented in the study-specific case report form (CRF).

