#### 13.1.4 Evaluation of response

All participants who reach initial restaging scan will be evaluable for response, as will subjects who are removed from study prior to initial restaging due to clinical disease progression. Patients removed from study prior to initial restaging for reasons other than disease progression are not considered evaluable for response. Each participant should be assigned one of the following categories: 1) complete response, 2) partial response, 3) stable disease, 4) progressive disease, 5) early death from malignant disease, 6) early death from toxicity, 7) early death because of other cause, or 9) unknown (not assessable, insufficient data). By arbitrary convention, category 9 usually designates the "unknown" status of any type of data in a clinical database.

Subjects who are removed from protocol prior to first restaging for reasons other than toxicity or disease progression may be replaced.

All conclusions should be based on all eligible participants. Subanalyses may then be performed on the basis of a subset of participants, excluding those for whom major protocol deviations have been identified (e.g., early discontinuation of treatment, major protocol violations, etc.). However, these subanalyses may not serve as the basis for drawing conclusions concerning treatment efficacy, and the reasons for excluding participants from the analysis should be clearly reported. The 90% confidence intervals should also be provided.

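### The success rule uses evaluable participants while conclusions are reserved for all eligible participants, and the plan does not say whether 91% or 31 governs below 34 evaluable

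*Combined protocol and SAP*

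**What the plan says.** Section 13.1.1 plans 34 participants and tests a CR rate of 95% against 81%, with 91% power and one-sided type I error 0.09. The decision rule is: "If at least 91% (31) of evaluable participants achieve complete responses, the treatment will be considered promising and worthy of further study". The same section defines who leaves the denominator: "Patients removed from study prior to initial restaging for reasons other than disease progression are not considered evaluable for response". Early stopping also refers to evaluable participants: "If greater than 2 evaluable participants are seen not to have disease response (CR or PR) following brentuximab-AD therapy, the study will stop".

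Section 13.1.4 repeats the evaluability definition and then says: "All conclusions should be based on all eligible participants". Subset analyses are allowed, for example ones that leave out early discontinuation, but "these subanalyses may not serve as the basis for drawing conclusions concerning treatment efficacy". Replacement is optional and does not cover toxicity: "Subjects who are removed from protocol prior to first restaging for reasons other than toxicity or disease progression may be replaced".

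The plan is not consistent about what removal means:

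- Section 5.3: "Participants will be removed from study treatment when intercurrent illness, toxicity, inability to participate or a change in condition occurs".
- Section 5.5: "Participants will be removed from the study upon death or withdrawal of consent".
- Section 13.1.3 has participants with unacceptable toxicity leaving the study itself, not only treatment.
- Section 8.3 and the study calendar footnotes schedule a PET-CT about 14 days after the last dose for anyone who stops early, unless one was done within 28 days of stopping. Neither says whether that scan counts as the initial restaging.

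**The concern.** The verdict on the primary endpoint is an efficacy conclusion. Section 13.1.1 draws it from a set that leaves out some eligible participants, and 13.1.4 says conclusions may not be drawn that way. An analyst following one section departs from the other.

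The cut-off adds a second ambiguity. The printed percentage and count agree at 34. A participant removed before the cycle 2 scan for toxicity may be both non-evaluable and outside the replacement rule, so the evaluable number can fall below 34. The text does not then say whether 91% or 31 decides, or how 91% is rounded. In an open-label single-arm trial with one decision rule, those choices should not be left until the results are known. The plan also does not say whether 81% and 95% are rates among evaluable or among all eligible participants.

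**Working it through.** **Inputs.** From 13.1.1: N = 34, cut-off 31, null rate 0.81, target rate 0.95. The documents give no early-removal rate t, so every value of t below is an assumption.

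**Step 1: the plan's own figures.** With X ~ Binomial(N, p), type I error is P(X ≥ k | p = 0.81) and power is P(X ≥ k | p = 0.95). For N = 34 and k = 31 these are 0.0906 and 0.9119, matching the stated 0.09 and 91%. Neighbouring cut-offs do not match (30: 0.199/0.974; 32: 0.031/0.759). The stopping probabilities 0.97 and 0.24 reproduce as P(3 or more failures of 34) = 0.969 and 0.241, so the 0.09/91% statement ignores the stopping rule.

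**Step 2: fewer than 34 evaluable.** Strict means the proportion must reach 0.91 (0.91 × 33 = 30.03, so 31; 0.91 × 32 = 29.12, so 30). Rounded accepts a proportion that rounds to 91% (30/33 = 90.9%; 29/32 = 90.6%). Fixed keeps 31. Entries are cut-off: type I error/power.

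| Evaluable N | Strict 91% | Rounded 91% | Fixed 31 |
|---|---|---|---|
| 34 | 31: 0.091/0.912 | 31: 0.091/0.912 | 31: 0.091/0.912 |
| 33 | 31: 0.036/0.773 | 30: 0.103/0.919 | 31: 0.036/0.773 |
| 32 | 30: 0.042/0.786 | 29: 0.118/0.926 | 31: 0.010/0.520 |

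**Step 3: can the two sets disagree?** Take 30 CRs, 2 evaluable non-CRs and 2 early toxicity removals that are not evaluable. Among evaluable participants, 30/32 = 93.8%, which passes. Among all eligible, 30/34 = 88.2%, which fails. On the strict reading this needs at least two early removals, because 33 evaluable still requires 31. On the rounded reading one is enough. With a fixed count of 31, scoring removals as non-CR leaves the verdict unchanged.

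**Step 4: how often.** Let the evaluable N ~ Binomial(34, 1 − t), with no replacement, and let X ~ Binomial(N, c) be the CRs among them. A disagreement is X at or above the evaluable cut-off k(N) but below 31, so its probability is the sum over N of P(N) × P(k(N) ≤ X ≤ 30). Strict reading:

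| Assumed t | P(2 or more removals) | Disagreement, c = 0.95 | Disagreement, CR rate 0.81 |
|---|---|---|---|
| 1% | 0.045 | 0.014 | 0.002 or less |
| 3% | 0.272 | 0.103 | 0.010 to 0.019 |
| 5% | 0.512 | 0.235 | 0.021 to 0.060 |

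In the last column the lower value takes 81% as the evaluable rate (c = 0.81) and the upper as the all-eligible rate (c = 0.81/(1 − t)).

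**Step 5: overall type I error and power**, averaged over N. With 81% and 95% as evaluable rates and t = 3%, the strict reading gives 0.058/0.827 and the rounded reading 0.097/0.909. If 81% is the all-eligible rate, the strict type I error is 0.110 at 3% and 0.151 at 5%; with the count fixed at 31 it stays at 0.0906 for every t.

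**The case against.** **A cut-off can be derived.** A reader might infer that the plan gives no rule below 34. That goes too far: it prints a percentage and a count, and either yields a cut-off at any N. What is missing is which one governs and how the percentage is rounded.

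**Early toxicity may not remove anyone from the evaluable set.** Under 5.3 and 5.5 toxicity ends treatment, not study participation, and 8.3 then schedules a PET-CT that could serve as the first restaging. On that reading the shortfall that cannot be replaced shrinks mainly to early toxic death. This is a fair reading, but 13.1.3 says the opposite, so the documents do not settle it.

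**Early removals may be rare.** In the earlier 34-patient study described in 2.1, preliminary data had every patient in CR after two cycles. That supports a rate near zero. It is limited evidence: the data were immature, and 2.2 suggests that regimen included vinblastine. At 1% the disagreement probability is small.

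**The rounded reading nearly preserves the design.** With evaluable rates, 0.097/0.909 at 3% is close to what is stated. This stands. A reader might infer that the evaluable rule generally inflates false positives, and the documents do not support that. Material inflation needs 81% to be the all-eligible rate together with a percentage reading. Otherwise it is confined to the rounded cut-off at particular N (0.103 at 33, 0.118 at 32), while the strict reading mainly costs power.

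**An evaluable set is common in phase II trials.** Agreed; the objection is to the unreconciled sections, not to either set.

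**Conclusion.** The conflict between 13.1.1 and 13.1.4 is in the text and should be fixed before analysis. The design arithmetic is correct for 31 of 34, and nothing here shows the stated 0.09 and 91% to be wrong at that N. The defect is an undefined analysis set and an undefined form of the cut-off for the sole primary decision.

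Its size depends on the early-removal rate, which is unknown and may be near zero. On the strict reading with a 95% evaluable CR rate, the two sets disagree with probability 0.014 at 1%, 0.10 at 3% and 0.24 at 5%; if the CR rate is 81%, the figure is 0.06 or less throughout. Under a fixed count of 31 it is zero. These figures assume independent removals, no replacement, and early removals scored as non-CR in the all-eligible set. They also assume that early toxicity makes a participant non-evaluable, which the plan leaves open.

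**What to change.** 1. In 13.1.1, make all eligible treated participants the primary set, in line with 13.1.4, with success defined as 31 or more CRs at end of treatment out of 34. Score early removal, death before the end-of-treatment assessment and a missing end-of-treatment assessment as non-CR. State that an interim CR alone does not count, unless the sponsor specifies otherwise.
2. Print one integer cut-off for each other N that ineligibility or replacement could produce, taking the smallest count that keeps type I error within the stated 0.09 as rounded: 33: 31 (0.036/0.773); 35: 32 (0.079/0.904); 36: 33 (0.069/0.896). Keeping 31 at N = 35 would give 0.179. State whether replaced participants stay in the denominator.
3. Report the evaluable-only CR rate as a labelled sensitivity analysis, and state which set the stopping rule uses. The choice matters: with a 95% response rate among restaged participants and an assumed 3% removal rate, the chance of 3 or more failures is 0.227 among evaluable participants and 0.506 if early removals count as failures.
4. State which set the 81% and 95% rates refer to. If 95% was meant for restaged participants, restate the power at 31 of 34 using 0.95 × (1 − t): 0.86, 0.72 and 0.57 at assumed removal rates of 1%, 3% and 5%.
5. Reconcile what removal from study means across 5.3, 5.5, 8.3, the study calendar footnotes and 13.1.3, including whether the early-discontinuation PET-CT counts as the initial restaging.

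Equally acceptable: keep the evaluable set as primary, print integer cut-offs with exact type I error and power for N of 34 and below, and amend the all-eligible sentence in 13.1.4.

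Cost: text edits and no new data. Under the first option the reported CR rate may be slightly lower, and the power statement may have to come down as in item 4, which is more than an editorial change if early removals are not rare. The alternative avoids that but needs more cut-offs.
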